12.4 Reporting of Adverse Events

The Investigator is responsible for ensuring that all AEs and SAEs are recorded in the source document, AE CRF, and/or SAE form, and reported to the Sponsor in accordance with protocol instructions.

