12.4.1 Adverse Event Reporting Period

All significant medical conditions including signs/symptoms of the underlying diagnosis found during the screening period and up to randomization will be captured as medical history. Any event/condition related to participation in the trial but not related to underlying or concomitant disease that is noted after screening up to the randomization date will be captured as a non-treatment emergent AE.

Any event/condition noted once the subject is randomized will be captured as an AE. All AEs and SAEs regardless of attribution will be collected until at least 30 days following the last administration of study treatment or initiation of new therapy, whichever is earlier. At the last scheduled visit, the Investigator should instruct each subject to report to the Investigator any subsequent SAEs that the subject's personal physician believes could be related to prior study treatment. Any related non-serious AE occurring after the reporting period may be reported at the discretion of the Investigator.

AEs and SAEs related to study drug that persist >30 days after the last study drug dose should be followed until resolution or until they return to baseline, stabilize, the subject is lost to follow-up, or it has been determined that the study treatment or participation is not the cause of the AE/SAE. Resolution of AEs and SAEs (with dates) should be documented on the AE CRF and SAE form (if applicable) and in the subject's medical record to facilitate source data verification. For some SAEs, the Sponsor or its designee may follow up by telephone, facsimile, electronic mail, and/or a monitoring visit to obtain additional case details deemed necessary to appropriately evaluate the SAE report (eg, hospital discharge summary, consultant report, or autopsy report).

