Any AE that results in hospitalization or prolonged hospitalization should be documented and reported as an SAE unless specifically instructed otherwise in this protocol.

i. Pregnancy

If a female partner of a male subject in the study becomes pregnant while her partner is receiving investigational therapy or within 6 months after the last dose of study, a Pregnancy form should be completed and faxed to the Sponsor’s Drug Safety Department or its designee within 24 hours of learning of the pregnancy, using the fax numbers listed in the Study Manual.

Abortion, whether therapeutic, or spontaneous, will be reported on a Pregnancy Report form and faxed to the Sponsor according to the instructions in the Study Manual. If the abortion meets seriousness criteria (see Section 12.5, Serious Adverse Event Definition), this information will be captured on the AE CRF and SAE form.

Any congenital anomaly/birth defect in a child born to a female subject or to a female partner of a male subject exposed to the investigational product should be recorded and reported as an SAE.

j. Overdose Reporting

Overdoses must be reported to the Sponsor on an AE CRF and an SAE form for tracking purposes and will be considered a protocol violation. Overdose is defined as any study drug dose administered above the intended dose for the cohort assignment. Additional instructions for reporting overdose information will be provided by the Sponsor at the time of notification.

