12.7 Serious Adverse Events Notification

For all SAEs, regardless of suspected causality, an SAE form must be completed (or faxed if using paper form) within 24 hours of discovery of the event to:

DRUG SAFETY

Fax toll free: See Study Manual for Fax Number

Any fatal or life-threatening (ie, imminent risk of death) event that is attributed by the Investigator to the investigational product must be telephoned to Drug Safety immediately, followed by submission of written case details on an SAE form within 24 hours.

SAEs occurring any time after study participation that are considered by the Investigator to be possibly related to study drug must also be reported. The following are important points to remember when completing the SAE form:

- If complete information is not available, at a minimum, subject identifier, suspect drug, site identifier, event or outcome, and Investigator assessment of causal relationship to study drug should be provided.
- A rationale for the causality assessment of an SAE should always be included, so that a better understanding of the event can be compiled.

- Follow-up information, such as laboratory reports, discharge summaries, autopsy reports, and information concerning outcome of the event should be submitted by revising the SAE form as soon as the information becomes available. Copies of source documents with subject identifiers redacted should be submitted only when they are written in English. If source documents are not in English, the Investigator must summarize the source documents, providing a complete English narrative that includes a description of the events as it evolved, the results of all diagnostic procedures performed, treatments administered, and outcome of the event. A query regarding a follow-up report should be answered within 5 working days from receipt of the query.
- Appropriate diagnostic tests and therapeutic measures are to be performed as necessary and reported on the SAE form.
- All SAEs must be reported to the IRB/Independent Ethics Committee, if applicable. See ICH GCP E6, Section 4.11.1.

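### Protocol 12.4.3 item i requires the 24-hour Pregnancy form only for partners of male subjects; the first report of an uncomplicated pregnancy in a female subject has no mandatory form or expedited limit

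*Protocol*

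**What the plan says.** The pregnancy rule is item i of Protocol 12.4.3. Its first sentence begins "If a female partner of a male subject in the study becomes pregnant while her partner is receiving investigational therapy", extends to 6 months after the last dose, and requires a Pregnancy form to be faxed to Drug Safety within 24 hours of the site learning of the pregnancy. Two further sentences in the item are wider. One reads "Abortion, whether therapeutic, or spontaneous, will be reported on a Pregnancy Report form and faxed to the Sponsor" and is not limited to partners. The other starts "Any congenital anomaly/birth defect in a child born to a female subject or to a female partner", so it names female subjects, and makes the event an SAE.

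The general rules are in 12.4, 12.4.1 and 12.7:

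- 12.4.1: "Any event/condition noted once the subject is randomized will be captured as an AE".
- 12.4.1: "All AEs and SAEs regardless of attribution will be collected until at least 30 days following the last administration of study treatment", or until new therapy starts if that is earlier.
- 12.4.1, after that period: "Any related non-serious AE occurring after the reporting period may be reported at the discretion of the Investigator".
- 12.4: AEs are to be "reported to the Sponsor in accordance with protocol instructions", with no time limit given there.
- 12.7: "For all SAEs, regardless of suspected causality, an SAE form must be completed", within 24 hours. This limit is for SAEs.

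Women are enrolled (5.3, criterion 6), and pregnant women are excluded (5.4, criterion 7). Women of childbearing potential must use contraception until at least 3 months after the last dose (6.3.3). They are tested after dosing on SAD Day 8 (7.3.6) and at 7 and 28 days after the last MAD dose (7.4.12). The SAP only lists the test results (4.10.2.8).

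**The concern.** The protocol expects women in the trial, tests them for pregnancy after dosing, and names them in its birth-defect rules. Yet the sentence that sets a form and a clock for a new pregnancy leaves them out. Followed exactly, indirect exposure through a male subject must reach the sponsor on a dedicated form within 24 hours. Direct exposure of a woman who inhaled the drug carries no such duty. The protocol gives no reason for the difference.

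The trial is described as first in human (13.1), and systemic absorption of the inhaled product is anticipated (2.0). Prompt notice of a directly exposed pregnancy is therefore at least as useful as notice of a partner's. What is at stake is safety reporting, not inference.

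**Working it through.** There is no figure in the plan to reproduce. The check compares the rules for the two groups and then sizes the uncovered time.

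**Rules side by side**

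| Situation | Partner of a male subject | Female subject |
|---|---|---|
| New uncomplicated pregnancy, during treatment and the AE period | Pregnancy form, 24 hours (12.4.3 i) | Ordinarily a non-serious AE (12.4.1); no time limit (12.4) |
| New uncomplicated pregnancy, from the end of the AE period to 6 months | Pregnancy form, 24 hours (12.4.3 i) | No explicit rule; related non-serious AEs are discretionary (12.4.1) |
| Abortion | Pregnancy Report form (12.4.3 i) | Same |
| Birth defect | SAE (12.4.3 i, 12.5), so 24 hours (12.7) | Same |

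The groups differ only in the first two rows. Pregnancy as such is not a listed seriousness criterion in 12.5, so 12.7 does not automatically apply. The instruction given to subjects at the last visit (12.4.1) concerns later SAEs only.

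**Scheduled tests against the AE period**

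The minimum is 30 days after the last dose. SAD: 7 ≤ 30. MAD: 7 ≤ 30 and 28 ≤ 30. A positive scheduled test therefore falls inside the period unless new therapy ends it earlier. For those cases what is missing is the form and the 24-hour limit, not capture.

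**Length of the period with no explicit rule**

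Assumptions: AE collection stops at 30 days; 6 calendar months are 181 to 184 days; 3 calendar months are 89 to 92 days.

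- Partner rule beyond the AE period: 181 − 30 = 151 to 184 − 30 = 154 days.
- Part of that inside the woman's own minimum contraception period: 89 − 30 = 59 to 92 − 30 = 62 days.

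**Expected number of pregnancies**

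Formula: women × annual failure rate × years at risk. Section 5.2 gives 64 subjects, or about 96 if every cohort expands. Section 6.3.3 requires a failure rate below 1% per year with consistent and correct use. Assumptions: every woman can conceive, the rate is at the 1% ceiling, and the time at risk is 4 weeks plus 3 months, about 0.33 years (too long for SAD subjects, who receive one dose).

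- Half of subjects are women: 32 × 0.01 × 0.33 = 0.11 to 48 × 0.01 × 0.33 = 0.16.
- All subjects are women: 64 × 0.01 × 0.33 = 0.21 to 96 × 0.01 × 0.33 = 0.32.

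Even the extreme case is well below one pregnancy over that window. Imperfect contraceptive use, or the months after contraception may stop, would raise the figure.

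**The case against.** The strongest reply is that a female subject's pregnancy is far from invisible. Section 12.5 opens with any AE suggesting a significant hazard or contraindication, and it lets medical judgment class other important events as serious. An investigator could treat a pregnancy in a treated woman that way, which brings in the 24-hour limit of 12.7. That section also requires possibly related SAEs to be reported at any time after participation. Section 12.0 makes investigators responsible for alerting the sponsor to anything unusual, and eCRF entry (14.2) and the test listing provide further routes.

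This stands, and it rules out some stronger readings. A reader might infer that her pregnancy can receive no more than routine AE handling; 12.5 and 12.7 show otherwise. A reader might infer that the alert in 12.0 is slower than the Pregnancy form; it states no timing, so the documents do not support that. A reader might infer that no dedicated form ever reaches female subjects; the abortion sentence shows that one does. None of these routes, however, makes a dedicated or expedited first report mandatory for an uncomplicated pregnancy.

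Two further points have weight. The Study Manual was not available and may instruct sites on subject pregnancies, so what sites do in practice is unknown. Item i refers to it only for fax numbers and abortion reporting, so the protocol text itself remains incomplete. Also, the 6-month window is set for partners, and the protocol does not justify it for women, whose contraception minimum is 3 months. The 151 to 154 days describe the asymmetry; only 59 to 62 of them fall within the woman's required protection.

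**Conclusion.** The point holds in a limited form. The only 24-hour Pregnancy-form rule is confined to partners of male subjects, and nothing in the protocol or SAP gives a directly exposed woman a mandatory equivalent for the first report of an otherwise uncomplicated pregnancy. During the AE period the loss is the dedicated form and the clock. After it, the loss is any explicit rule, for about 151 to 154 days relative to partners if collection stops at 30 days.

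The practical yield is small, since well under one pregnancy is expected under the assumptions above. No endpoint, DLT or MTD rule, or analysis changes. It is still worth correcting: a written safety rule has the wrong scope, and a few words put it right. The conclusion concerns the protocol text and does not depend on the content of the Study Manual.

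**What to change.** In 12.4.3 item i, change the trigger to: *If a female subject, or a female partner of a male subject, becomes pregnant during the subject's treatment or within 6 months after the subject's last dose of study drug, ...* Keep the existing form, fax route and 24-hour limit. The 6-month window is the one the item already uses, and one window for both groups is simplest. The new wording also makes clear that the window runs from the last dose of study drug.

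The cost is a few words, a few extra reports, and approval by the IRB/IEC and country authorities (14.1). It can be carried in the next amendment. Follow-up of the pregnancy to outcome, and handling of study drug after a positive test, are separate decisions that the sponsor could settle at the same time.

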12.5 Serious Adverse Event Definition

An SAE is any AE that suggests a significant hazard, contraindication, side effect, or precaution regardless of the relationship to study drug. An SAE is any AE that results in any of the following outcomes:

- Death
- Life-threatening AE. This definition implies that the subject, in the view of the Investigator, is at immediate risk of death from the event as it occurred. It does not include an event that, had it occurred in a more severe form, might have caused death.
- In-subject hospitalization or prolongs existing hospitalization, except for hospitalization for planned post-dose sample collections
- Persistent or significant disability/incapacity (ie, the AE results in substantial disruption of the subject's ability to conduct normal life functions)
- Congenital anomaly or birth defect. This serious criterion applies if a congenital anomaly/birth defect is diagnosed in a child born to a female subject, or a female partner of a male subject exposed to the investigational product.
- Other important medical events. Medical and scientific judgment should determine whether an AE should be classified as serious in other situations, such as important medical events that may not be immediately life-threatening or result in death or hospitalization, but may jeopardize the subject or require intervention to prevent one of the outcomes listed in the definition above. Examples of such events include allergic bronchospasm requiring intensive treatment in an emergency room or at home, blood dyscrasias or convulsions that do not result in inpatient hospitalization, or the development of drug dependence or abuse.

All AEs that do not meet any of the criteria for serious should be regarded as **non-serious AEs**.

The terms “severe” and “serious” are not synonymous. Severity refers to the intensity of an AE (as in mild, moderate, or severe pain); the event itself may be of relatively minor medical significance (such as severe headache). “Serious” is a regulatory definition and is based on subject or event outcome or action criteria usually associated with events that pose a threat to a subject’s life or vital functions. Seriousness (not severity) serves as the guide for defining regulatory reporting obligations.

Severity and seriousness should be independently assessed when recording AEs and SAEs on the CRF and SAE form.

12.6 Suspected Unexpected Serious Adverse Reaction Definition

A SUSAR is a suspected unexpected serious adverse reaction. In order to be qualified as a SUSAR, the AE must meet 3 criteria: the event is serious, there is a certain degree of probability that the event is a reaction to the medical product being researched and the nature and severity of the reaction are not in agreement with the product information (ie, the reaction is unexpected as per the reference safety information). All SUSARs will be reported as required to the Competent Authorities of all involved European member states and to the Ethics Committee of the member states concerned.

12.7 Serious Adverse Events Notification

For all SAEs, regardless of suspected causality, an SAE form must be completed (or faxed if using paper form) within 24 hours of discovery of the event to:

DRUG SAFETY

Fax toll free: See Study Manual for Fax Number

Any fatal or life-threatening (ie, imminent risk of death) event that is attributed by the Investigator to the investigational product must be telephoned to Drug Safety immediately, followed by submission of written case details on an SAE form within 24 hours.

SAEs occurring any time after study participation that are considered by the Investigator to be possibly related to study drug must also be reported. The following are important points to remember when completing the SAE form:

- If complete information is not available, at a minimum, subject identifier, suspect drug, site identifier, event or outcome, and Investigator assessment of causal relationship to study drug should be provided.
- A rationale for the causality assessment of an SAE should always be included, so that a better understanding of the event can be compiled.

- Follow-up information, such as laboratory reports, discharge summaries, autopsy reports, and information concerning outcome of the event should be submitted by revising the SAE form as soon as the information becomes available. Copies of source documents with subject identifiers redacted should be submitted only when they are written in English. If source documents are not in English, the Investigator must summarize the source documents, providing a complete English narrative that includes a description of the events as it evolved, the results of all diagnostic procedures performed, treatments administered, and outcome of the event. A query regarding a follow-up report should be answered within 5 working days from receipt of the query.
- Appropriate diagnostic tests and therapeutic measures are to be performed as necessary and reported on the SAE form.
- All SAEs must be reported to the IRB/Independent Ethics Committee, if applicable. See ICH GCP E6, Section 4.11.1.

12.8 Expedited Reporting of SUSARs

- The Sponsor or its designee is responsible for notifying the investigational sites of all expedited SAEs (ie, 7/15 Day SUSARs) that occur during any clinical studies that are using the investigative compound. The Sponsor or its designee shall also notify Central Ethics Committees and Central IRB of SUSARs or significant risks to subjects, per country requirements. All SUSARs will be reported as required to the Competent Authorities of all involved European member states.
- The Investigator will notify local IRB or Local Ethics Committees (LECs) of SUSARs or significant risks to subjects, per local country requirements. The Investigator must keep copies of all AE information, including correspondence with the Sponsor or Local Ethics Committees on file.

All studies that are conducted within any European country will comply with the European Clinical Trial Directive 2005/28/EC, the Clinical Trial Directive 2001/20/EC and the Detailed Guidance CT-3 (2011/C 172/01).

12.9 Emergency Unblinding Procedure

In the event of a medical emergency, when knowledge of treatment assignment is needed for immediate medical management of the subject's health, Investigators can obtain unblinded treatment assignment through the centralized IWRS system at any time. Thorough documentation of the rationale for unblinding is required. Consultation of the study Medical Monitor is recommended for all unblinding requests.

13.0 STATISTICAL METHODOLOGY

13.1 General Considerations

A comprehensive Statistical Analysis Plan (SAP) specifies the statistical methodology, and table, figure and listing (TLF) formats for all aspects of the planned analyses. The SAP supports the

completion of Clinical Study Report (CSR) for this protocol. As the risk profile of QR-010 in humans is unknown and this is a first in human trial, all AEs will be considered in determining the safety profile of QR-010 unless obviously unrelated. As an early phase clinical study, exploratory analyses not necessarily identified in the SAP may be performed to support the clinical development program. Any post-hoc, or unplanned, analyses not identified in the SAP will be clearly identified in the CSR, in accordance with applicable Standard Operating Procedures (SOPs) of the sponsor.

13.2 Determination of Sample Size

This is a Phase 1 safety study designed to evaluate the safety, tolerability and PK of QR-010. The sample size is not based on power calculations. It is chosen based on clinical experience and considered to be adequate to fulfill the objectives of the study.

Approximately 64 subjects will be enrolled in the study, with 8 subjects per cohort (6 QR-010 and 2 placebo), 32 each in the SAD and MAD portions of the study. The exact number of subjects enrolled is dependent on whether any dose level are to be expanded due to the occurrence of DLTs.

13.3 Randomization and Blinding

13.3.1 Randomization Procedures

At screening, potential subjects will be randomized into the current enrolling cohort. In the event that there is both a SAD and MAD cohort enrolling in parallel, the subject may elect participation in either an open SAD or MAD cohort. All sites will be capable of and expected to enroll all cohorts of the study. Subjects who meet all of the inclusion criteria and none of the exclusion criteria will be eligible for randomization. Eligible subjects will be randomized on Day -1 by a centralized interactive web response system (IWRS), utilizing the randomization schedule generated by the designated unblinded statistician. The IWRS system will be used to assign dose level and treatment assignments to subjects, within the cohort type (SAD or MAD) selected by the subject at screening.

Within each dosing cohort, subjects will be randomized 3:1, QR-010 to placebo. At least one of the first two subjects enrolled in the first cohort will be randomized to receive QR-010.

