4.2 Study Design

The study is a multicenter, randomized, double-blind, and placebo-controlled Phase 1b SAD and MAD design. The subject, investigator, and site personnel (except pharmacist) will be blinded to treatment, while the sponsor will be unblinded. Sponsor personnel will be unblinded to subject

treatments in order to permit real-time interpretation of the safety, pharmacokinetic, and pharmacodynamic data. The site monitor will remain blinded to individual subject treatment allocation until all monitoring of study data has been completed. To minimize the potential for bias, individual subject treatment randomization information will not be released to the investigator or blinded study site personnel until the study database has been locked.

Eligible subjects with homozygous $\Delta F508$ CF will be randomized at a 3:1 ratio to receive either QR-010 or placebo via oral inhalation (nebulization). This study will be conducted in North America and select European countries.

[figure not shown]
The study includes 2 stages. The first stage is a single ascending dose-escalation (SAD) design to determine safety and tolerability of a single dose of QR-010. The second stage is a multiple ascending dose escalation (MAD) design to further assess the safety, tolerability, and exploratory efficacy of 12 doses of QR-010 over 4 weeks. All doses will be administered in a clinical setting.

For the SAD cohorts, subjects will receive the dose in an inpatient observation unit and be observed for a total 4 days, and will be discharged on Day 4. Subjects will return for PK and safety follow-up as an outpatient on Day 8 (End of Study Visit).

For the MAD cohorts, subjects will receive doses 1 through 12 in a clinic while under observation. On Day 1 and Day 3 subjects will be observed until 12 hours post dose. Following the last dose (dose 12), subjects will return twice for PK sampling, and will be evaluated 7 and 28 days after the last visit for this additional safety monitoring and sampling for PK.

A schematic of the study design is presented in Figure 3.

Figure 3: PQ-010-001 Study Schematic

Single Ascending Dose Escalation Cohorts: The first two subjects of each cohort may be dosed on the same day, at least 4 hours apart. If no significant AEs occur, the remainder of the cohort may be dosed at least 24 hours later, with at least 1 hour between subjects.

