After each single dose cohort, an independent Data Safety Monitoring Committee (DSMC) will review available safety data, including 7 days of follow up after administration of QR-010. Dose escalation may occur upon recommendation of the DSMC.

Multiple Ascending Dose Escalation Cohorts: The safety results from the single dose escalation portion of the study will support the initiation of the corresponding multiple dose escalation cohorts, as illustrated in [Figure 3](#).

After each multiple dose cohort, the DSMC will review available safety data, including 7 days of follow up after administration of the last dose of QR-010 (End of Treatment Visit). Dose escalation may occur upon recommendation of the DSMC.

Both Stages: Subjects must sign informed consent before any study-related procedures are initiated. Subjects will receive QR-010 by inhalation via the eFlow device.

Blood, urine and sputum samples will be obtained from all subjects to obtain PK data pre- and post-dosing.

Subjects will undergo clinical and laboratory assessments for safety. Subjects will be withdrawn from the study when intolerable toxicity occurs, or when the subject withdraws consent.

The schedule of assessments is summarized in Appendix 1 and 2.

AE profiles by cohort and dose escalation decisions by the DSMC are communicated to all study sites after DSMC review of cumulative and cohort-specific safety data.

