4.3 Dose Escalation

The single dose escalation scheme will test fill doses of 6.25 mg to 50 mg over 4 dose levels, and the multiple dose escalation scheme will test fill doses of 6.25 mg to 50 mg given thrice weekly (tiw) for 4 weeks ([Table 1](#)). As described in Section 2.2.1, the dose delivered to subjects via the eFlow device is < 80% of the fill dose, hence the delivered doses that correspond to the dose escalation schemes are shown in [Table 1](#).

Table 1: Dose Escalation

| Dose Cohort | Fill Dose (mg) | Estimated Exposure Dose < 80% of Fill Dose (mg) |
|-----------------------------------------------------------------|----------------|----------------------------------------------------|
| Single Dose Cohorts | | |
| 1 | 6.25 | 5 |
| 2 | 12.5 | 10 |
| 3 | 25 | 20 |
| 4 | 50 | 40 |
| Multiple Dose Cohorts (administered tiw for 4 Weeks) | | |
| 5 | 6.25 | 5 |
| 6 | 12.5 | 10 |
| 7 | 25 | 20 |
| 8 | 50 | 40 |

tiw = thrice weekly (three times per week)

Dose escalation will initially proceed in single subject cohorts from fill dose level 1 (6.25 mg) to fill dose level 4 (50 mg).

Initiation of MAD Cohort 5 will be based on the safety profile of SAD Cohort 2. Initiation of Cohort 6 will be based on the safety profiles of Cohorts 3 and 5. Similarly, initiation of Cohort 7 will be based on the safety profiles of Cohorts 4 and 6, and finally, the initiation of Cohort 8 will be based on the safety profile of Cohort 7. The first dose between subjects in each cohort must be separated by a minimum of 4 hours.

For the single dose cohorts 1 to 4, dose escalation to the next cohort may occur upon recommendation of the DSMC after the subjects have been observed for at least 7 days and no DLTs have occurred or, if a DLT has occurred, per the dose escalation rules in Section 4.5. For the multiple dose cohorts 5 to 8, dose escalation to the next cohort may occur upon recommendation of the DSMC after the subjects have been observed for at least 7 days after the last dose (End of Treatment Visit). If a DLT occurs in any cohort, the AEs and DLTs will be reviewed by the Investigator and the DSMC before dosing can continue in that cohort. In addition, if ≥ 2 subjects experience a decrease in absolute FEV₁ of $\geq 15\%$ from baseline in any cohort, the data will be reviewed by the DSMC before dose escalation can continue.

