## 2.4. Randomization Methodology

Within each dosing cohort, subjects will be randomized 3:1, QR-010 to placebo.

The randomization is performed using a centralized interactive web response system (IWRS).

Study drug will be administered in a double-blind fashion. Study drug and placebo are both clear, colorless, and odorless aqueous solutions. Subjects, Investigators and study site staff will be blinded to treatment assignment. However, due to the requirement for study pharmacist(s) to prepare the various study drug dilutions depending on the dosing cohort to which a given study subject is assigned, the study pharmacist(s) will be unblinded to treatment assignment.

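### The two-subject, 24-hour step applies to every SAD cohort, but a QR-010 recipient in the first pair is guaranteed only in the first cohort

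*Protocol*

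**What the plan says.** Protocol section 4.2 describes the step for the SAD portion: "The first two subjects of each cohort may be dosed on the same day, at least 4 hours apart". If no significant adverse events occur, "the remainder of the cohort may be dosed at least 24 hours later, with at least 1 hour between subjects". The step is written for each SAD cohort.

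Protocol section 13.3.1 sets 3:1 allocation within each cohort and adds: "At least one of the first two subjects enrolled in the first cohort will be randomized to receive QR-010". The guarantee goes no further than that cohort. Section 13.2 fixes the split at 6 QR-010 and 2 placebo in a cohort of 8.

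SAP section 2.4 says only: "Within each dosing cohort, subjects will be randomized 3:1, QR-010 to placebo". Neither document gives a block size or extends the first-pair rule to cohorts 2 to 4.

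**The concern.** The 24-hour wait tells the trial something about a new dose only if at least one of the first two subjects received it. The protocol recognises this for the first cohort. The same reasoning applies to cohorts 2, 3 and 4. Each doubles the previous fill dose (6.25, 12.5, 25, 50 mg), and each is the first use of its dose in the study, because under section 4.3 the MAD cohorts reach a dose only after the SAD portion has. Section 13.1 describes the trial as first in human with an unknown risk profile. No reason is given for stopping the guarantee at the first cohort.

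If both placebos fall in the first pair, a clean 24 hours is reassuring only about placebo. The rest of the cohort may then proceed on it, and under the 6:2 split every one of those six subjects is on QR-010.

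**Working it through.** **Inputs**
- Cohort size 8, with 6 QR-010 and 2 placebo (Protocol 13.2).
- Four SAD cohorts, of which one carries the guarantee (Protocol synopsis and 13.3.1), leaving 3 without it.
- Spacing after the 24-hour wait: at least 1 hour between subjects in Protocol 4.2; at least 4 hours between first doses within a cohort in Protocol 4.3.
- Block size: not stated, so treated as an assumption and varied.

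**The plan's own figures.** 6/2 = 3:1; 4 × 8 = 32 per portion; 8 × 8 = 64 in total. These agree with section 13.2. The documents give no probability for the make-up of the first pair.

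**One block of 8.** Two placebos can be placed in 8 positions in C(8,2) = 28 ways.

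| QR-010 recipients in first pair | Placements | Probability |
|---|---|---|
| 2 | C(6,2) = 15 | 53.6% |
| 1 | 6 × 2 = 12 | 42.9% |
| 0 | C(2,2) = 1 | 3.6% |

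The pair therefore includes a QR-010 recipient with probability 27/28 = 96.4%. Across cohorts 2 to 4, taken as independent, the chance of at least one all-placebo pair is 1 − (27/28)³ = 10.3%.

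**Blocks of 4 (3:1).** Each block holds one placebo, so two cannot fall in positions 1 and 2. The chance is 0% per cohort and 0% overall.

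**Simple 3:1 randomization, for reference.** 0.25² = 6.25% per cohort and 1 − 0.9375³ = 17.6% for the three. This would not deliver the fixed 6:2 split, so it is left out of the range.

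**What follows from an all-placebo pair.** All six remaining subjects receive QR-010. Six starts have five intervals. At 1 hour apart, the sixth starts 5 × 1 = 5 hours after the first exposure; at 4 hours apart, 5 × 4 = 20 hours. Both are under 24 hours, so at minimum spacing no exposed subject has been followed for 24 hours before the last subject starts. The 1-hour and 4-hour statements need reconciling in their own right; the conclusion is the same under either.

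**The case against.** The limit to the first cohort may be deliberate. That cohort is the first human exposure to the product. Every later SAD cohort opens only after the DSMC, which sees unblinded data (Protocol 12.1), "will review available safety data, including 7 days of follow up after administration of QR-010" in the preceding cohort. Section 2.2.1 calls the dose scheme highly conservative. After a dose-limiting toxicity, "the AEs and DLTs will be reviewed by the Investigator and the DSMC before dosing can continue in that cohort". SAP 2.5.2 sends Grade 2 or higher events of interest to the DSMC before the cohort is complete. The sponsor is unblinded "in order to permit real-time interpretation of the safety, pharmacokinetic, and pharmacodynamic data", so it could notice an all-placebo pair. SAD subjects are observed as inpatients, with repeated spirometry on the dosing day. The gap also depends on a schedule that the documents do not show, and losing the 24-hour look further requires near-minimum spacing.

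Much of this stands, and it keeps the point modest. It does not close the gap. DSMC review of the preceding cohort concerns a lower dose. Review of toxicities and events of interest acts only once something has happened. Nothing requires the sponsor to check the first pair. Blocks of 4 would remove the risk, but they would also make the first-cohort sentence unnecessary, so its presence gives no support to assuming them. None of these safeguards ensures that someone receives the new dose before the 24-hour look.

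**Conclusion.** The concern holds as a gap in a safeguard; the two protocol sections do not contradict each other. Sections 4.2 and 13.3.1 differ in scope, and nothing in either document bridges them. The size is small: 0% to 3.6% per cohort, and 0% to 10.3% for at least one of SAD cohorts 2 to 4. This assumes that the 6:2 split is kept, that allocation uses either blocks of 4 or one block of 8, that cohorts are independent, and that the first cohort means Cohort 1. It does not extend to the MAD cohorts, for which no two-subject step is written.

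There is a second, smaller gap. The guarantee concerns the first two subjects enrolled, while the step concerns the first two dosed. Subjects randomized on Day -1 may leave untreated and be replaced (13.3.3), so the two orders can differ. The change should be made because it protects a first-in-human safety step at very little cost.

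**What to change.** In Protocol 13.3.1, apply the guarantee to each SAD cohort instead of the first only, and word it for the first two subjects dosed. Repeat the rule in SAP 2.4. Generate each remaining 6:2 list so that positions 1 and 2 hold at least one QR-010 assignment.

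Because the pair may be at two sites and dosing order may not follow list order, have someone already unblinded, such as the unblinded statistician, confirm that the first two dosed include a QR-010 recipient, without disclosing assignments. The sponsor and DSMC should settle in advance what follows if that cannot be confirmed. A visible pause could tell blinded staff that the pair was placebo and hence that the remaining six are all on QR-010.

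The cost is one sentence, one excluded placement in 28 per list, and one unblinded check per cohort. Blinded staff who know the rule learn that the first pair is not all placebo, a cost already accepted for the first cohort.

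SAP 4.10.2.6 (Table 27) already lists free-text organism entries, which suggests that enrolment was under way. For cohorts already dosed, check whether any first pair was all placebo and report the result in the study report; this may be the part that still matters.
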